
6. Overall, in the past week, how would you rate the severity of the appearance of this cNF?
 
 Not at all severe  Mild  Moderate  Severe  Very severe

7. In the past week, how much have you had to be careful to avoid irritating this cNF?
 
 Never  Rarely  Sometimes  Often  All of the time

8. In the past week, how much has this cNF bothered you?
 
 Never  Rarely  Sometimes  Often  All of the time

9. In the past week, how self-conscious were you about this cNF?
 
 Not at all  A little bit  Moderately  Quite a bit  Extremely

At Visit 8, in addition to the items above each subject will assess their experience since they started using the study medication with global items graded using the following scales:

1. a) Please choose the response below that best describes the change in this cNF overall since you started using the study medication:
 
 Very much better Much better A little better No change A little worse Much worse Very much worse 
b) Do you consider this change in your cNF overall to be meaningful?
 
 Yes No

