9.3.5.3 Endpoints

The safety endpoint is to determine the safety of treatment with NFX-179 Gel ([REDACTED] and [REDACTED] or Vehicle Gel applied QD for 182 days of treatment. The results of dermal safety and local tolerability assessments including pain/burning, itching, erythema, edema, scabbing/crusting, and vesiculation/erosion will be summarized by treatment group and visit. The evaluation of adverse events will be based on summaries and listings of adverse events by treatment group, as described below under Safety Analyses. If tumor independence is confirmed as discussed above, the primary efficacy endpoint will be a dichotomized analysis conducted on the proportion of tumors achieving a reduction from baseline volume of at least 50%. A Chi-square analysis at the tumor level will be performed as the primary analysis between vehicle and each active treatment group. Otherwise, if tumor independence is not confirmed, the primary efficacy endpoint will be analyzed at the subject level. The primary efficacy analysis will then be a dichotomized Chi-square Responder analysis at the subject level. It will be based on the proportion of subjects considered to be Responders, where a Responder is defined as a subject

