for whom at least 5 treated tumors showing the greatest tumor-level percent reduction from baseline volume have a percent reduction from baseline of at least 50%. A Chi-square analysis with contrasts as outlined above will be used. At the subject-level analysis, an Analysis of Variance will also be used to analyze the per-subject mean percent of tumor responders, with contrasts as described above. Treatment groups may also be compared using appropriate mixed-model logistic regression incorporating both tumor- and subject-level information. Supplementary analysis similar to those described above will also be conducted based on threshold reductions from baseline volume of at least 25%, 30%, 60% and 75%. The first secondary efficacy endpoint is to determine the clinical efficacy of NFX-179 Gel defined as the mean percent change in neurofibroma volume after 182 days of treatment based on tumor volume derived from ruler measurements. Analyses of Variance will be conducted both on the tumor level and the subject level, including the contrasts as described above. The determination of whether the tumor-level or subject-level analysis will be considered preferentially will be based on the outcome of the tumor independence assessment described above. The non-primary analysis will be considered as a supplementary analysis. Additional secondary efficacy endpoints include the analysis of change from baseline in the Physician's Tumor Assessment grade and the Subject's Self-Assessment grade after 182 days of treatment. These will be analyzed analogously to the primary endpoint using an Analysis of Variance and contrasts described above. In addition, for each assessment dichotomized analyses will be conducted on the proportion of tumors achieving a grade of Clear, the proportion of tumors achieving a grade of either Clear or Almost Clear, the proportion of tumors achieving at least a grade 1 improvement, and also a 2 grade or greater improvement from baseline after 182 days of treatment. Treatment groups will be compared using separate Chi-square analyses. An appropriate mixed-model logistic regression may also be used, as well as an ANOVA analysis of within-subject averaged results across tumors. Contrasts as described above will be used.

Analyses similar to those described above will be conducted based on tumor area and tumor length.

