Efficacy analyses at post-baseline visits prior to Day 182 where efficacy data are collected will also be performed using the models described above. These will be considered exploratory in nature.

Analyses will also be performed to examine the strength of relationship between tumor volume Responders (as defined above), and PROM Responders defined as subjects indicating improvement based on Visit 8 Supplementary PROM items and also indicating the improvement was meaningful. These analyses will include appropriate correlation evaluations for dichotomous parameters, as well as odds-ratio analyses and related 95% confidence limits. These analyses will be conducted at both tumor and subject levels.

The psychometric properties of the PRO measure will be analyzed under a separate statistical analysis plan.

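### Volume response and subject-rated meaningful change are linked only through yes/no variables, which loses precision and does not show where meaningful change begins

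*Combined protocol and SAP*

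**What the plan says.** All references are to the combined protocol and SAP.

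- **Volume variable (Section 9.3.5.3).** At tumor level it is "the proportion of tumors achieving a reduction from baseline volume of at least 50" percent. At subject level the Responder rule is: "at least 5 treated tumors showing the greatest tumor-level percent reduction from baseline volume have a percent reduction from baseline of at least 50" percent.
- **Subject-rated variable (Section 9.3.5.3).** "PROM Responders defined as subjects indicating improvement based on Visit 8 Supplementary PROM items and also indicating the improvement was meaningful".
- **Method (Section 9.3.5.3).** "These analyses will include appropriate correlation evaluations for dichotomous parameters, as well as odds-ratio analyses and related 95% confidence limits". Also: "These analyses will be conducted at both tumor and subject levels". No coefficient is named. No hypothesis, alpha, power or expected correlation is given for this analysis.
- **What is collected (Section 7.3.3).** At Visit 8, for each Target cNF, the subject is asked: "Please choose the response below that best describes the change in this cNF overall since you started using the study medication". There are seven ordered answers. A second item of the same form asks about size. Each is followed by a separate Yes/No item, for example "Do you consider this change in your cNF overall to be meaningful".
- **What is already derived (Section 9.3.5.3).** The first secondary endpoint is the "mean percent change in neurofibroma volume after 182 days of treatment based on tumor volume derived from ruler measurements". It is planned for comparing treatment groups, not for relating volume to the subject's ratings.

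**The concern.** This is the analysis in Section 9 that ties the 50% volume rule of the primary endpoint to what subjects call meaningful. It enters volume as a yes/no variable when the percent change is on file. Reductions of 51% and 95% then count the same. Reductions of 45% and 0% also count the same.

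Two things follow. The strength of the relationship is estimated less precisely than the data allow. And one table at 50% shows whether that cut is associated with meaningful change, but not whether another cut would fit better or at what reduction subjects begin to report meaningful change. The second consequence needs no assumption about rates or correlation.

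**Working it through.** **The plan's own figures.** None is given for this analysis. The power of at least 90% in Section 9.1 belongs to the primary comparison and cannot be reproduced, because both responder rates are redacted. The numbers of subjects are consistent: 1 − 150/168 = 10.7% dropout.

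**Inputs from the documents.** 150 completers (Section 9.1); 10 Target cNFs each, so about 1,500 tumors; intraclass correlation bound 0.25 (Section 9.3.5.1).

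**Assumptions.** Bivariate normal latent variables with correlation ρ; all arms pooled; volume Responders 10%, 20% or 35%; PROM Responders 30% or 50%. Power of a two-sided 5% test serves only as a yardstick for precision.

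**Formulas.**
- Both variables cut, with shares p and q: φ = (p11 − pq)/√[p(1−p)q(1−q)], where p11 is the bivariate normal probability of being above both cuts.
- Volume continuous, PROM Responder still binary: r = ρ·f(z_q)/√[q(1−q)], where f is the normal density at the cut z_q.
- Power ≈ Φ(atanh(r)·√(n−3) − 1.96).
- Tumor level: design effect 1 + 9 × 0.25 = 3.25, so effective n = 1,500/3.25 ≈ 462. This is an approximation at the bound.

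**Worked case: ρ = 0.3, p = 20%, q = 30%.**
- p11 = 0.0913, so φ = (0.0913 − 0.06)/√(0.16 × 0.21) = 0.0313/0.1833 = 0.171.
- Odds ratio = (0.0913 × 0.5913)/(0.1087 × 0.2087) = 2.38.
- r = 0.3 × 0.3477/0.4583 = 0.228.
- n = 150: 2x2 power = Φ(0.1727 × 12.12 − 1.96) = 55%. With volume continuous, Φ(0.2317 × 12.12 − 1.96) = 80%. The gain is 25 points.
- n = 462: Φ(0.1727 × 21.42 − 1.96) = 96%, against more than 99%. The gain is 4 points.

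**Gain in points from keeping volume continuous (same formulas, all settings).**

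| ρ | n = 150, Responders 20–35% | n = 150, Responders 10% | n = 462, Responders 20–35% | n = 462, Responders 10% |
|---|---|---|---|---|
| 0.2 | 15–22 | 25–29 | 17–26 | 38–42 |
| 0.3 | 18–30 | 37–45 | 2–5 | 12–15 |
| 0.4 | 9–19 | 28–37 | 0 | 1–2 |
| 0.5 | 2–6 | 11–21 | 0 | 0 |
| 0.6 | 0–1 | 2–9 | 0 | 0 |

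A simulation at n = 150 (2,000 runs per setting, chi-square against Mann-Whitney) agrees. At ρ = 0.3 power is 40–65% for the 2x2 table and 78–85% with volume continuous. Across ρ = 0.2 to 0.4 the gain is 10–44 points.

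**Phi.** Even with perfectly agreeing ranks, the largest possible phi is √[lo(1−hi)/(hi(1−lo))], where lo and hi are the smaller and larger share. For 10% against 50% this is √(0.05/0.45) = 0.33. For 20% against 50% it is √(0.10/0.40) = 0.50. The limit does not apply to the odds ratio.

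**The case against.** The case on the other side is strong in several places.

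- **No test is planned.** The aim is to describe strength of relationship with confidence limits. This stands: the loss is one of precision, and power is only a way to express it.
- **The 2x2 table is a fair question in itself.** It checks whether the primary 50% rule agrees with subject-rated meaningful change, and a 45% reduction rated meaningful is a discordance it ought to reveal. This stands, so the table should stay.
- **The PROM Responder is not merely a cut of the 7-level scale.** It also needs the Yes/No item, which is binary as collected. A Spearman correlation with the seven levels leaves that item out. The ratings are made per tumor, and no subject-level 7-level score is defined. This stands, so that correlation can only supplement.
- **Tumor level carries more information.** This stands, as the table shows.
- **Other material may cover the gap.** The 25%, 30%, 60% and 75% thresholds might be read as carrying over to this analysis, but they would only add more 2x2 tables. The separate psychometric SAP is not available and may hold a full-scale analysis. The exit interview study (Section 4.1) also concerns perception of meaningful change. None of these prespecifies a full-scale analysis in the visible text.

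A reader might infer that the plan gives up 10 to 50 points of power outright, or that it understates the association. The documents support neither. The first holds only for a weak to moderate assumed correlation and mainly at subject level. The second would be true of phi, which the plan does not name. The planned odds ratio is on another scale, and a tetrachoric coefficient, which the wording allows, targets the underlying correlation.

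**Conclusion.** The concern holds in a limited form. The visible plan relates volume to meaningful improvement only through yes/no variables. It therefore loses precision and, with volume cut at 50%, does not show where meaningful change begins.

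The loss is worth roughly 10 to 40 points of power at 150 subjects if the latent correlation is 0.2 to 0.4. At 0.5 it is about 2 to 6 points, or 11 to 21 if only 10% are volume Responders, and it is smaller still at 0.6. At tumor level it is near nil from 0.4. These figures depend on assumed rates and correlations and on an approximate design effect. A near-nil gain means that the association would be detected either way. It does not mean that the 2x2 table locates the threshold.

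Severity is minor. The PROM endpoint is exploratory, and no primary or secondary result, error rate or sample size rests on this analysis.

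**What to change.** In Section 9.3.5.3:

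1. Keep the 2x2 odds ratio at the 50% cut, and name the correlation coefficient (phi or tetrachoric).
2. Add a tumor-level logistic regression and ROC curve of PROM Responder (improved and meaningful, still binary) on continuous percent reduction in volume. Use subject-clustered standard errors or a bootstrap that resamples subjects. Report the reduction that best separates meaningful from not meaningful, with its confidence interval. State which of the two Visit 8 items, overall or size, defines the PROM Responder.
3. As a supplement at tumor level, add the Spearman or polyserial correlation of percent change with each 7-level item, with mean percent change and confidence interval per level. Allow for clustering by subject here too.

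The cost is SAP wording and a few more exploratory tables. No new data, visits or subjects are needed. If the separate psychometric SAP already contains these analyses, a cross-reference is enough.

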9.3.6 Safety Analyses

Subjects will be assessed for the occurrence of new and ongoing AEs. Descriptions of AEs will include the dates of onset and resolution (if resolved), maximum severity, seriousness, and action taken regarding the study drug, corrective treatment, outcome, and investigator's assessment of causality. All AEs will be recorded and classified using terminology from the Medical Dictionary for Regulatory Activities (MedDRA). All reported treatment-emergent AEs (TEAEs), defined as any AE with an onset on or after the date of first study drug application, will be summarized by treatment group, the number of subjects reporting TEAEs, system organ class, preferred term, severity, and relationship to study drug. When summarizing TEAEs by severity or relationship to study drug, each subject will be counted only once within a system organ class or a preferred term using the event with the greatest severity or causality, respectively, within each category. All reported SAEs will be summarized by treatment group, the number of subjects reporting SAEs, system organ class, preferred term, severity, and relationship to study drug.

All information pertaining to AEs noted during the study will be listed by subject and will include a verbatim description of the event as reported by the investigator, as well as the preferred term, system organ class, start date, stop date (if stopped), seriousness, severity, action taken regarding the study drug, corrective treatment, outcome, and relationship to the study drug. In addition, a listing of subjects who prematurely discontinued from the study due to AEs will be provided as well as a listing of subjects who reported an SAE.

Changes from baseline in safety laboratory values, local tolerability assessments, and vital sign measurements will be summarized with descriptive statistics for each treatment group at

all applicable study visits.

Shift tables will be presented for changes in safety laboratory values to summarize laboratory test results collected at all visits. Normal ranges established by the central laboratory will be used to determine the shifts. A listing of all out-of-range laboratory test results at any assessment time point will also be provided. Determination of clinical significance for all out-of-range laboratory values will be made by each investigator and included in the listing. In addition, a listing of all clinically significant laboratory test results will be provided.

Other safety assessments, including vital signs, physical examination data and LTA data will be summarized by treatment group.

9.4 Missing Data

Unless otherwise specified, summaries and analyses will be based on non-missing data, with the number of non-missing observations included in the summary. The use of methods to impute missing data, including LOCF, is discussed above.

9.5 Sub-Group Analyses

Exploratory efficacy investigations may be carried out based on subject gender, subject age, time since onset of NF1 diagnosis and/or cNF appearance, cNF classification, baseline tumor size, study medication compliance, and other factors.

Exploratory safety investigations may be carried out based on subject gender and age.

Exploratory sub-group analyses of safety parameters may be conducted based on time since CNF diagnosis, age at onset, study medication use per day, and other parameters.

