An investigational center staff member will weigh each study medication tube when dispensed, at each study visit, and when returned using the provided scale (or equivalent). The study medication container weight must be reported to the nearest 0.1 g. The study medication tubes must be weighed with the label attached and the cap on and without any other packaging.

At Visit 2, the study medication tube dispensed to the subject must be weighed pre subject application of study medication and post subject application of study medication.

The scale used to weigh the study medication tubes must be calibrated, according to the instructions provided for the scale, and the calibration documented, each day the scale is used, prior to use. Any scale that does not pass the calibration test must not be used to weigh the study medication.

5.6.7 *Route of Administration, frequency and treatment period*

The study medications are applied topically to each Target cNF, once daily for 182 days (26 weeks).

5.6.8 *Study medication application*

The study medications are for external, topical use on each Target cNF only and on the appropriate study subject only.

To perform a study medication application the subject should:

- Wash her/his hands before starting the application
- Avoid applying the study medication to any open wounds or obviously infected skin
- Apply an amount of the assigned study medication sufficient to cover each Target cNF with a thin layer of the study medication
- Gently rub in the study medication until no visible accumulation is evident
- Wash her/his hands after completing the application.

The subject must apply study medication to the entire area of each Target cNF limiting exposure to the un-affected skin surrounding the cNF.

At Visit 2, an investigational center staff member will instruct the subject on the proper application technique and observe the subject's study medication application to ensure proper

application technique and record the time the subject completes the application to the last Target cNF as the Application Completion Time. A staff member will monitor the subject for adverse events for at least 20 minutes after the Application Completion Time.

Subjects should continue QD application of the assigned study medication to each Target cNF for 182 days (26 weeks) with 18-30 hours between applications.

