5.6.9 Dose Modification

Subjects should not modify the study medication application procedure or frequency unless instructed to do so by the investigator. All application modifications must be reported on the appropriate CRF page.

If any significant study medication intolerance or safety issue occurs, after consulting with the Medical Monitor, the investigator or designee may direct the subject to reduce the study medication application frequency. If the subject cannot perform QD applications to a specific Target cNF(s), the subject may continue study medication treatment of <10 Target cNFs selected by the investigator for the duration of the study after consultation and approval from the Medical Monitor. If the subject cannot perform QD applications to any Target cNF for a total of 25 days,

the subject must be removed from the study. The total of 25 days applies to individual Target cNFs and is not an aggregate of non-treatment days of each Target cNF. Each Target cNF that meets or exceeds 25 total days of non-treatment cannot restart treatment. All 10 Target cNFs must be evaluated at each visit per protocol requirements regardless of study medication application frequency.

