5.8 Study medication adherence

Adherence with the study medication application frequency and application of an appropriate amount of study medication will be monitored by questioning the subject regarding adherence at each visit and by measuring the weight of the study medication tubes when dispensed to the subject, at each treatment period visit and when collected from the subject.

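### Section 9.5 allows exploratory subgroups by compliance and by gel use per day; outcomes can change both, so these splits can dilute and sometimes reverse the relation of use to outcome

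*Combined protocol and SAP*

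**What the plan says.** Section 9.5 has separate lists of exploratory factors for efficacy and safety. The efficacy list runs from gender and age to "cNF classification, baseline tumor size, study medication compliance, and other factors". The third paragraph reads "Exploratory sub-group analyses of safety parameters may be conducted based on time since CNF diagnosis, age at onset, study medication use per day", followed by other parameters. All of these analyses are optional. Neither compliance nor use per day is given a definition, time window, denominator or cut-off, and neither is marked as a post-randomization quantity.

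Four other sections determine how these two variables behave:

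- **5.6.9 Dose Modification.** For significant intolerance or a safety issue, after consulting the Medical Monitor, "the investigator or designee may direct the subject to reduce the study medication application frequency". Where daily application to specific tumors is not possible, "the subject may continue study medication treatment of <10 Target cNFs selected by the investigator". A tumor that reaches 25 non-treatment days stays off treatment.
- **8.1.1 Adverse Event.** Worsening of a Target cNF assessment, such as local tolerability, is reported as an adverse event (AE) only if study medication is interrupted or discontinued, or other therapy is needed.
- **5.6.8 Study medication application.** The subject is told: "Apply an amount of the assigned study medication sufficient to cover each Target cNF with a thin layer of the study medication". Daily application continues on the site of a cleared tumor.
- **5.8 Study medication adherence.** Adherence is followed by questioning and "by measuring the weight of the study medication tubes when dispensed to the subject", at treatment visits and on return.

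**The concern.** Age, gender and baseline tumor size are fixed before treatment. Compliance and use per day are not, and the protocol itself gives outcomes a route into both.

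- **Safety.** A subject who reacts may be told to apply less often or to fewer tumors. Average use then falls because of the event, and events collect in the low-use group. For local reactions the link is partly built into the definition, since under 8.1.1 a fall in use is one of the things that makes the worsening reportable.
- **Efficacy.** If compliance means grams used, a fully adherent subject whose tumors shrink may return heavier tubes and be classed as a poor complier.
- **Between arms.** If irritation lowers compliance mainly on active gel, active compliers are a selected group and vehicle compliers are not selected in the same way. Randomization no longer protects that comparison.

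Section 9 names no extent-of-exposure summary, so these subgroups are its only named analyses relating amount of gel used to outcome. A table suggesting that more gel means fewer AEs, or that compliers respond less, could mislead the reading of exposure.

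**Working it through.** The plan gives no figure for these analyses. Its power statement (9.1) rests on redacted responder rates and does not bear on this point. The check is therefore a simulation. From the documents come 182 treatment days, the 25-day limit (25/182 = 13.7%), 10 tumors, 168/3 = 56 subjects per arm, and the 50% response threshold. All rates and spreads are assumed.

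**1. Safety, every AE lowers use.** Intended daily use is log-normal with SD 0.15 or 0.30 on the log scale. AE risk is 20% at typical use, with odds ratio (OR) 1.00, 1.22 or 1.49 per SD of log use. An AE occurs at a uniform time t, after which a fraction c of use is lost:

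observed use per day = u × [t + (1 − c)(182 − t)] / 182

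c is 10%, 13.7%, 30% or 50%. For equal-sized tumors, stopping 1, 3 or 5 of 10 gives 10%, 30% or 50%. Subjects are split at the median. Selected results, AE rate in the high-use and low-use halves:

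| OR per SD | c | SD | By intended use, high / low | By observed use, high / low |
|---|---|---|---|---|
| 1.00 | 13.7% | 0.15 | 20.0% / 19.9% | 14.2% / 25.7% |
| 1.00 | 50% | 0.15 | 20.0% / 20.0% | 5.7% / 34.3% |
| 1.22 | 13.7% | 0.15 | 22.7% / 17.6% | 16.7% / 23.6% |
| 1.22 | 10% | 0.30 | 22.8% / 17.7% | 20.6% / 19.9% |
| 1.49 | 13.7% | 0.30 | 25.8% / 15.6% | 22.7% / 18.7% |

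With no true effect, all 8 settings show fewer AEs at high use. With a true harmful effect, 12 of 16 reverse; the other 4, all with small cuts, only shrink the difference.

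**2. Safety, only some AEs lower use.** This uses 56 subjects per arm, a coefficient of variation of use of 20–40%, a true OR of 2 per doubling of use, and use halved or stopped after a modifying AE. The percentages are the share of simulated trials in which low use looks worse:

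| AEs that lead to modification | Wrong direction |
|---|---|
| All | 77–100% |
| 25% | roughly 27–55% |
| 10% | roughly 18–36% |
| All, loss capped at 25 days | roughly 42–84% |
| 25%, loss capped at 25 days | roughly 20–40% |

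Part of each figure is chance in an arm of 56.

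**3. Efficacy.** The fraction of days applied, a, has mean 0.88 and SD 0.08. Log volume change at Day 182 is −g·a plus noise, with g = 0.3, 0.6 or 1.0 and noise SD 0.3 or 0.6. SD of log baseline area is 0 or 0.3. Gel per application follows area, taken as volume^(2/3), so halving the volume gives 0.5^(2/3) = 0.63, or 37% less area. With g = 0.6, noise SD 0.6 and area SD 0.3, response rates in the high and low halves are:

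- by days applied: 41.0% / 36.7% (the true direction)
- by grams per day: 23.0% / 54.7%
- by grams per day over baseline area, full period: 5.2% / 72.4%

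Across 12 settings, both gram measures reverse every time and days applied never does.

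**4. Compliers across arms.** With no drug effect, and assuming that 15–30% of subjects are reactors with prognosis worse by 0.5–1 SD, type I error among compliers is 6–22%. No document supports those inputs, so this only illustrates the selection.

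**The case against.** The strongest reply is that these analyses are optional and exploratory, and that a competent analyst would read them with care. That stands as to weight: no primary or secondary result uses either variable.

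A second reply concerns size. AEs include unrelated events, 5.6.9 reserves modification for significant problems, and the 28-day study (2.2.2) reported no treatment-related events and mostly mild, transient local findings. If few AEs change use, the bias is much smaller, as step 2 shows. This also stands for AEs overall. It is weaker for local reactions, because 8.1.1 ties reporting to interruption, discontinuation or other therapy. The 25-day rule limits how long use can stay reduced on a tumor still under treatment. It does not limit the loss from tumors stopped for good while others continue.

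A third reply is that compliance may mean days applied. Section 5.8 lists questioning as well as weight, and 5.6.8 keeps daily application after clearance, so response would then have little route into the measure. Shrinkage may also be mainly in height: going from 2 mm to 1 mm can halve the volume with length and width unchanged, and the gel needed then hardly falls. Both points stand. The plan does not say which measure applies.

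A reader might infer that the trial's dose-response conclusion is compromised. The documents do not support that: 9.3.5.2 tests dose response by contrasts between randomized groups, which 9.5 does not touch. A reader might also infer that the splits would almost always mislead. That requires every AE to cut use substantially and compliance to be defined by weight, and the documents establish neither.

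**Conclusion.** The concern holds in a limited form. Section 9.5 places two post-randomization variables among baseline factors, and the protocol's own rules let intolerance and, under a weight measure, tumor response change them. Splitting on them can dilute the relation of use to AEs or response and in some settings reverse it. Comparing active with vehicle compliers is not a randomized comparison.

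The mechanism comes from the documents; the size does not. It depends on how many AEs lead to modification, how far use falls, and how compliance is defined. The simulations show possible direction, not an expected magnitude. With days applied as the measure, reversal of the efficacy result is not expected. The change is worth making because the remedy is cheap, but it concerns exploratory output only.

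**What to change.** 1. In 9.5, remove study medication compliance and study medication use per day, and limit subgroup factors to those fixed before first application.
2. Add a descriptive exposure table by arm on the Safety Population: days applied, grams used per visit interval, frequency reductions and tumors stopped.
3. If a use-outcome relation is wanted, specify a landmark analysis within each active arm. Measure use over a fixed early interval, for example Visit 2 to Visit 4. Relate it only to later outcomes, among subjects with no modification by then, and label it descriptive and non-causal.
4. Measure use as days applied or as grams scaled to baseline tumor area. Do not divide by current area: cleared tumors are still treated, so responders would look like heavy users. Days applied is the safer choice. Baseline scaling alone does not remove the bias (step 3 of the working), and 2.2.2 reports volume reduction by Day 28, so some can remain even in an early window.
5. Do not compare active compliers with vehicle compliers.

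The cost is SAP wording and one table. Tube weights (5.6.6), dimensions (7.2.1) and application modifications (5.6.9) are already recorded. The sponsor should confirm that missed days from the adherence questions are captured as counts, which the 25-day rule already needs. The simple complier table is lost, and the landmark analysis leaves out early events.
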